8.4 Treatment Discontinuations

Patients should discontinue treatment with the study treatment, but remain on the study for adequate follow-up, for any of the following reasons:

- Patients may discontinue study drug treatment at any time if the patient, Investigator, or Laurent determines that it is not in the best interest of the subject to continue treatment.
- Unacceptable toxicity associated with treatment (see below stopping rule, section 8.4.1)
- Clinically significant lab abnormalities or adverse events that, in the Investigator's judgment, would preclude continued treatment.

The reason for treatment discontinuation will be noted on the e-CRF.

If a patient discontinues treatment due to unacceptable toxicity or any other safety reason, that patient should either continue to be assessed according to the planned visit schedule for safety and for relevant efficacy parameters, or at the minimum, attend a Treatment Discontinuation Visit four (4) weeks after having received the last dose of study drug.

8.4.1 Individual Patient Stopping Rule

The following should be used as a guide for the Investigator to determine if the study drug administration is to be interrupted based on toxicity (see Section 11.1.1.3 on Study Drug Action Taken, for more detail on documentation):

- A subject develops a medical condition that requires prolonged concomitant therapy with a prohibited medication or prolonged interruption of the study drug;

- Occurrence of a SAE that could be attributable to the drug (at least *probably* causality relationship), and causes discontinuation of study drug for more than 3 weeks;
- High and unexpected frequency and/or severity of “at least probably related” adverse events that in the judgment of the Investigator, requires withdrawal from the study.

8.5 Replacement of Patients

Patients who are withdrawn or lost-to-follow-up prior to Baseline, or who do not meet the Baseline criteria, will be replaced to ensure 136 eligible patients are enrolled into the study. Patients who withdraw after Baseline will not be replaced.

9 STUDY CONDUCT

9.1 Timing of Assessments

All questionnaires must be performed before any other assessment at the clinic visits with the CFQ-R questionnaire performed first, followed by the Night Vision Questionnaire (NVQ) and the Patient self-assessment form of the Matouk Disease Score (at selected sites only). For the remaining assessments, the following assessments must be performed (if possible) in the following order when more than 1 assessment is planned at a particular time point:

1. 12-lead ECG recordings
2. Vital signs
3. Pulmonary function tests (FEV₁) and Sputum Induction
4. Safety laboratory assessments (i.e., blood draws)
5. PK sampling

9.2 Study Visits and Procedures

9.2.1 Screening and Eligibility Assessments (Visit 1, Day -28 to -1):

Within 28 Days of randomization, interested CF patients will undergo a screening session, Visit 1:

1. Verification of identity and age;
2. Prior to any study specific screening activities, all potential patients will sign the Study Informed Consent Form (ICF). The consent forms will comply with all applicable regulations governing the protection of human subjects. An ICF Form, approved by Laurent Pharmaceuticals and the site's institutional review board (IRB) or ethics committee (EC), must be used. At this point, the site assigns a “subject/patient number” to each patient, in order of screening. This will serve to identify the patient for the entire study participation. This is not the randomization number, which is generated by the IWRS at Visit 2, at time of randomization;
3. Confirmation of the CF diagnosis will be obtained, with proper genetic data if available;
4. Verification of all inclusion and exclusion criteria;
5. Obtain medical history including history of prior pulmonary infections, pulmonary exacerbations and their causative pathogens, all recent and current medications and therapies, non-prescription drug intake, pancreatic enzyme quantities (where applicable) as well as vitamin supplementation (types and quantities). Particular attention will be put on obtaining the history of presence or absence of *PsA* in throat or sputum cultures, the dates of start of oral/IV antibiotics taken to treat PEx episodes, both in the 12 months prior to screening. This will help establishing a background exacerbation *PsA* and PEx pattern;
6. Verification of the medications against list of disallowed medications and associated ban periods;

7. Body weight, height, with BMI calculated;
8. Complete Physical examination;
9. A 12-lead ECG;
10. Vital signs including respiratory rate, oxygen saturation and body temperature;
11. A pulmonary function test comprising at a minimum FEV₁, to be performed under the care of a trained study personnel. Three FEV₁ measurements will be collected and the best of three FEV₁ values (according to American Thoracic Society standards) will be recorded. Central review of the expiratory loops will be performed to ensure accurate baseline FEV₁;
12. Eligibility-defining laboratory tests including at a minimum, urinalysis (dipstick), hematology, serum chemistry, plasma retinol and retinol-binding protein, and pregnancy test if applicable;
13. A Night Vision Questionnaire will be self-administered;
14. Complete ophthalmological examination (includes examination of visual acuity, examination for amblyopia, examination of eyelids, conjunctiva, cornea, pupillary reactions to light and accommodation, low contrast visual function (Contrast Sensitivity), specific dark adaptation tests (see note in Section 11.5), lens, vitreous humor, fundus examination of retina and retinal vessels, fundus visualization of optic nerve and macula), will also serve as the baseline exam;
15. Sputum will be induced using hypertonic saline for the assessment of the CFU for *PsA*. Patients with known intolerance to hypertonic saline will not undergo the procedure, as judged by their treating physician. A precise set of instructions will be provided and applied across sites to minimize sampling variations and ensure sputum sample quality;
16. Screening may be split into more than one visit and all results must be available prior to randomization so that the study Investigator can determine eligibility and schedule the baseline visit.

9.2.1.1 Repeat performance of screening assessment(s)

Repetition of individual screening assessment(s) that did not meet eligibility criteria is not permitted with the following exceptions:

- If there is clear and documented evidence of a laboratory error (e.g., hemolyzed sample) or equipment malfunction, collection of a repeat sample for the appropriate laboratory test or assessment may be permitted;
- Due to the unstable nature of CF, any clinically significant laboratory test abnormality, but deemed transient by the Investigator, may be retested within the screening window.

If repeat values of the individual assessment(s) are within the eligibility criteria and completed within the screening window, then the patient is eligible for the study.

9.2.1.2 Rescreening

Patients may only be rescreened with the approval of the medical monitor. If a patient is rescreened, all screening assessments will be repeated except CF genotyping (if not already in the patient's medical history), and the ophthalmologic examination (if performed within the last 3 months). If a patient is rescreened, the screening window will begin once the first rescreening assessment has been initiated.

9.2.2 Baseline and First Dosing Visit (Visit 2, Day 1)

1. Eligible CF patients will be invited to the study site for the baseline procedures and first dosing. This visit must be within 28 days of screening otherwise all or a part of expired screening procedures will need to be repeated/updated (see Section 9.2.1.2);
2. Confirmation of continued eligibility by verification of the inclusion/exclusion criteria, review of the results of the screening safety laboratory tests including plasma retinol and retinol-binding protein, performance of baseline vital signs, urine pregnancy test for women, and focused physical examination;

3. Pulmonary function tests (FEV₁). The actual baseline FEV₁ value for the study will be the average of the screening's best value and the best value obtained during the baseline visit as long as the screening and baseline FEV₁ values are within 15% of each other. A higher difference in FEV₁ % predicted indicates a lack of acceptable pulmonary function stability and the patient should not be randomized on study;
4. Body weight, with BMI calculated;
5. At sites that participates in the bone density exploratory assessment, the first 24 patients who consent to the additional procedure of measuring bone density prior to and after the study treatment, will undergo their baseline assessment; being not exclusionary, this test may be scheduled within a few days of first dose but not after;
6. Baseline Quality of Life questionnaire will be filled out (CFQ-R);
7. At select sites participating in the investigation of the Matouk Disease Score, the Baseline Score will be determined;
8. Pre-dose blood sampling and urine collection for baseline safety laboratory tests, pregnancy test if applicable, plasma retinol and retinol-binding protein, lipidomic tests, ceramides, metabolipidomic tests, systemic bone formation/resorption markers, inflammation and oxidative stress markers;
9. All eligible patients will be stratified according to 1- Baseline FEV₁, 2- PEx number in the prior year, and 3- Co-administration of Kalydeco® (ivacaftor), Orkambi® (ivacaftor/lumacaftor), Symdeko® (ivacaftor/tezacaftor) or another commercially available CFTR modulator product, and equally allocated/randomized to either a daily dose of 300mg of LAU-7b, (as 3 x 100 mg oral hard gelatin capsules), or matching placebo.
10. Randomized patients will receive their first dose of study treatment under supervision, under fed condition and will receive a 21-day supply of study treatment. Patients will be discharged after tolerability of the first dose has been observed (minimum one hour post-dose).

9.2.3 Report of a pulmonary exacerbation (any time during the study)

Patients will be instructed to adhere to the standard of care in use at the institution, that is to contact their treating physician and team when they feel that they are experiencing a change in symptoms for at least 3 days (ease of breathing, cough, quantity and nature of sputum, activity tolerance). If indicated based on the initial interaction, the study team will invite the patients to the clinic to do a proper assessment and determine a course of action such as antibiotic treatments. Being an efficacy variable, particular attention will be put on obtaining precisely the start of any antibiotics, whether oral or IV. If an IV antibiotic is prescribed and the patient can attend the study site prior to starting the IV antibiotics and after the planned end of antibiotics, this will trigger a set of pre- and post-antibiotic treatment additional blood sampling for study-related markers, a pulmonary function test (FEV₁), as well as measurements of weight, with BMI calculated. Details are presented in Section 9.3 "Pulmonary Exacerbation Reporting and Evaluation".

9.2.4 Telephone contacts (around Days 10, 38, 66, 94, 122 and 150)

All patients will be contacted by phone on or about 10 days post-first dose of each cycle, to inquire about potential adverse events. Specific attention will be put on probing about adverse events related to visual disturbances or dermatological problems as follows: "How is your vision since the last visit/phone call?" and "How is your skin since the last visit/phone call?" Actions may be taken if necessary.

9.2.5 End-of-Cycle Visits (Visits 4, 5, 6 and 7, on Days 21(window: Days 21-22), 49(window: Days 49-51), 77(window: Days 77-79), 105 (window: Days 105-107) and 161(window: Days 161-163)

Special attention will be put on reports of symptoms/signs of pulmonary exacerbation by patients as this may trigger a set of additional assessments. Details are presented in Section 9.3 "Pulmonary Exacerbation Reporting and Evaluation". Adverse events will be monitored and captured at all visits.

1. **On Days 21, 77 and 161 visits**, the following assessments will also be done:
 - a. Focused physical examination;
 - b. Ophthalmological evaluation: The NVQ will be self-administered, and if Grade 2 severity criteria is met or exceeded (On Day 77 visit, the ophthalmological examination is planned, independently of the NVQ result), a full ophthalmological examination will be performed (includes dark adaptation tests), and if clinically indicated by the ophthalmologist, an electroretinogram will also be performed, in order to evaluate any potential ophthalmological condition developed during the treatment cycle);
 - c. Vital signs and 12-lead ECG;
 - d. Pulmonary function tests (FEV₁);
 - e. Pre-dose blood sampling and urine collection for safety laboratory tests, pregnancy test if applicable, plasma retinol and retinol-binding protein;
 - f. Study drug compliance check and concomitant medications;
 - g. Body weight, with BMI calculated.
2. **On Days 49 and 105 visits**, the following assessments will also be done;
 - a. Safety laboratory tests;
 - b. Pulmonary function test (FEV₁);
 - c. Concomitant medications.
3. **On Days 21 and 77 visits only**: All patients will return prior treatment boxes, for accountability purposes and will receive re-supply of study treatment for their next treatment cycle(s);
4. **On Days 21 and 161 visits only**: Blood sample for the determination of fenretinide plasma through (C_{min}) concentrations, plasma lipidomic, ceramides and metabolipidomic tests, markers of inflammation and oxidative stress;
5. **On Day 77 visit only**: Ophthalmological evaluation: Complete ophthalmological examination (includes dark adaptation tests). If clinically indicated by the ophthalmologist, an electroretinogram will also be performed;
6. **On Days 77 and 161 visits only**, the following assessments will be done:
 - a. Sputum will be induced using hypertonic saline for the assessment of the CFU for *PsA*;
 - b. CFQ-R questionnaire to be filled out;
 - c. At select sites participating in the investigation of the Matouk Disease Score, the Score will be determined.
7. **On Day 161 visit only**: systemic bone formation/resorption markers.

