Biochemical and hematological safety parameters were not affected by fenretinide at all dose levels. The reduction of serum retinol levels as compared to baseline appeared to be smaller in CF patients than those reported in other patient populations. Two (2) SAEs occurred during this study, both classified as unrelated to fenretinide with one related to CF disease (exacerbation with hospitalization) and easily explained by the condition of the patient, and one related to a concomitant disease (varicella case).

[REDACTED]

[REDACTED]

[REDACTED]

[REDACTED]

[REDACTED]

[REDACTED]

[REDACTED]

[REDACTED]

In conclusion, the safety and tolerability of fenretinide in adult CF patients was comparable with the reported safety profile associated with the use of this drug in other patient populations over similar or longer periods of treatment, and with comparable systemic exposure levels. The study Safety Review Committee has acknowledged the safety of the drug in this patient population and has recommended 300mg QD as the dose to be tested in Phase II trial ³.

PHARMACOKINETIC RESULTS:

Following single and multiple doses of fenretinide as LAU-7b, plasma exposure (C_{max} and AUC) increased with dose, and this increase was judged dose proportional (p -value > 0.05). The plasma concentration profile indicated first-order elimination kinetics.

[REDACTED]

Generally, inter-patient variability was modest for the fenretinide PK parameters, even with the small sample size. After a single dose, the mean $t_{1/2}$ was consistent across the dose range studied with values ranging from 6.99 h to 7.50 h. Mean $t_{1/2}$ values at PK steady-state ranged from 8.25 h to 16.65 h.

EFFICACY RESULTS:

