9.4 Study Drug Treatment

The total duration of study treatment is 6 cycles of 21 consecutive days of either LAU-7b or placebo treatment each followed by a 7-days treatment-free period. This represents approximately 24 weeks in total.

During the study, eligible CF patients aged 18 years and older will be randomized, after stratification according to 1- FEV₁ severity categories, 2- Number of PEx episodes in prior year, and 3- Co-administration or not of Kalydeco®, Orkambi®, Symdeko® or another commercially available CFTR modulator product, using a 1:1 allocation to LAU-7b 300 mg per day or matching placebo, in a double blind fashion. Treatment assignments will be determined through the IWRS system.

In all cases, the study treatment will be administered on top of current Standard of Care therapies.

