9.5 Treatment and Protocol Compliance

Patients are expected to receive oral daily doses based on the protocol schedule and have all procedures done within the allowable time windows (detailed in the schedule of events, page 10).

Regardless of allowable visit windows, study drug treatment cycles should always be 28 days, each consisting of 21 consecutive days of either LAU-7b or placebo treatment, followed by a 7-days treatment-free period. In the event a patient misses to start a cycle on time, he/she should start the cycle as soon as possible and inform the study site staff so that future visit schedule be adjusted accordingly.

In the event a patient misses a scheduled assessment visit, this should be rescheduled for the earliest possible date. Patients who are persistently noncompliant may be withdrawn from the study at the investigator's or the sponsor's discretion.

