10.7 Fenretinide Through Samples

In this study, patients will contribute PK samples for the determination of steady-state fenretinide through concentrations (C_{min}), 4-methoxy fenretinide (4-MPR), a significant but inactive metabolite as well as those

of 4-oxo-fenretinide, a minor active metabolite of interest. Blood samples for fenretinide and metabolites C_{min} will be obtained pre-dose or 24 hours post-previous dose, at the time of the safety lab sampling, on Days 21 and 161 time points, as listed in the Schedule of Events, Page 10. More specifically, since this is a double blind placebo controlled study, all patients whether or not on fenretinide, will undergo the sampling procedure. Results will not be communicated to blinded staff, in order to maintain the study blind, unless required for emergency reasons.

Patients will be informed at time of screening of the mandatory nature of the PK procedure and pre-dose requirements (arrive fasting at the clinical site on Days 21 and 161). All the blood collection and sample processing must be carried out in reduced light condition. Details of collection, storage and processing are provided in the Study Reference Manual and when instructed to do so, prepare all the samples in need of shipment to the designated central lab [REDACTED], for dispatch to the bioanalytical laboratory, [REDACTED] Laval, Quebec, Canada.

10.8 Other exploratory biomarkers: ceramides, metabolipidomics, systemic bone formation/resorption markers and oxidative stress markers

Blood samples for the determination of other biomarkers, such as ceramides, metabolipidomic, systemic bone formation/resorption markers and oxidative stress markers, will be obtained at the time points listed in the Schedule of Events, Page 10.

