The Pharmacokinetic (PK) Population will include all patients randomized to the LAU-7b treatment group and provided the C_{min} blood samples. This population will serve as the basis for the between-group comparison of the steady-state fenretinide pharmacokinetics grouped according to the *a priori* stratification factors and to compare the results with those obtained during the prior Phase Ib study.

The Healthy Control Population will consist of 20 healthy controls. The data for these patients will be collected by Laurent Pharma, and provided to JSS Medical Research for assessment of

demographic and pharmacodynamic parameters (AA, DHA), the latter for use in the Pharmacodynamic analyses.

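### The Day 161 visit window runs to Day 163, so a cycle 6 Cmin sample can be drawn about 48 h after the last dose, against Protocol 10.7, and no SAP rule sets such a sample apart

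*Protocol*

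**What the plan says.** **Visit windows.** The heading of Protocol 9.2.5 gives "Days 21(window: Days 21-22" for the first end-of-cycle visit and "161(window: Days 161-163" for the last. Item 4 of that section places the Cmin draw at these two visits only.

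**Dosing calendar.** Protocol 9.4: "The total duration of study treatment is 6 cycles of 21 consecutive days". Protocol 9.5: "Regardless of allowable visit windows, study drug treatment cycles should always be 28 days, each consisting of 21 consecutive days". A late visit therefore does not extend dosing.

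**Sampling definition.** Protocol 10.7 says that Cmin samples "will be obtained pre-dose or 24 hours post-previous dose" on Days 21 and 161. Footnote 10 of the Schedule of Events (Protocol Section 2, repeated in SAP Table 1) says pre-dose on those two days.

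**Analysis.** Cmin at the end of cycles 1 and 6 is a secondary endpoint (Protocol 7.1.3, SAP 2.8.1.2). The PK population in SAP 3.3 takes "all patients randomized to the LAU-7b treatment group" who provided the Cmin samples, and Protocol 12.2 agrees. SAP 3.17 tabulates Cmin by sampling day and compares the stratification groups within the LAU-7b arm. The PK population definition adds a comparison with Phase Ib. None of these sections mentions actual time since the last dose.

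**The concern.** The visit window and the sampling definition disagree. The protocol allows a visit on a day when the sample can no longer be a 24 h trough, and the SAP does not say what happens to that sample. Of the five end-of-cycle visits, only Day 21 has a one-day window. Days 49, 77 and 105 have two-day windows but no Cmin draw. Day 161 has both a two-day window and a Cmin draw.

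Any resulting error goes one way: a late sample reads low. It would lower the cycle 6 summary and, at that time point, the stratum summaries and the comparison with Phase Ib. In Phase Ib the Day 21 blood samples were taken about 24 h after the previous dose (Protocol 5.4.4.1). A reader who sets cycle 6 beside cycle 1 could take a sampling artefact for falling exposure.

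**Working it through.** **Step 1: when the last dose falls.** Cycle c starts on Day 28(c − 1) + 1 and its 21st dosing day is 20 days later.

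| Cycle | First dose | Day 10 of cycle | Last dose |
|---|---|---|---|
| 1 | 1 | 10 | 21 |
| 2 | 29 | 38 | 49 |
| 3 | 57 | 66 | 77 |
| 4 | 85 | 94 | 105 |
| 5 | 113 | 122 | 133 |
| 6 | 141 | 150 | 161 |

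This reproduces the plan's own calendar. The last-dose column matches the end-of-cycle visit days for cycles 1-4 and 6 (cycle 5 has no visit). The day-10 column matches the call days in Protocol 9.2.4: "All patients will be contacted by phone on or about 10 days post-first dose of each cycle".

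**Step 2: time since last dose at each permitted visit day**, for a patient on schedule.

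| Visit day | Previous dose | Interval | Meets Section 10.7? |
|---|---|---|---|
| 21 (pre-dose) | Day 20 | about 24 h | yes |
| 22 | Day 21 | about 24 h | yes |
| 161 (pre-dose) | Day 160 | about 24 h | yes |
| 162 | Day 161 | about 24 h | yes |
| 163 | Day 161 | about 48 h | no |

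Only Day 163 fails. It is neither pre-dose, since no dose follows, nor 24 h after the previous dose. A late cycle start does not remove the gap, because Section 9.5 moves the visit schedule with it.

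**Step 3: how low a 48 h sample reads.** Protocol 5.4.4.1 reports first-order elimination, with mean half-life "values at PK steady-state ranged from 8.25 h to 16.65 h". The fraction of the 24 h trough left after a further 24 h is f = 2^(−24/t½):

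- t½ = 8.25 h: f = 2^(−2.91) = 0.133
- t½ = 16.65 h: f = 2^(−1.44) = 0.368

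A Day 163 sample therefore reads about 13-37% of the 24 h trough, which is 63-87% too low.

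**Step 4: effect on the mean.** If a share x of cycle 6 samples is drawn on Day 163, and those patients would otherwise have had the same mean trough as the rest, the mean changes by −x(1 − f). The documents do not give x, so the shares below are assumptions.

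| Assumed x | t½ = 16.65 h | t½ = 8.25 h |
|---|---|---|
| 10% | −0.10 × 0.632 = −6.3% | −0.10 × 0.867 = −8.7% |
| 25% | −0.25 × 0.632 = −15.8% | −0.25 × 0.867 = −21.7% |

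If no sample is drawn on Day 163, the change is zero.

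**The case against.** - **No sentence accepts a 48 h sample.** Section 10.7 and footnote 10 define the sample, and the PK population can be read as requiring one that meets that definition. A reader might infer that the SAP chose to treat 48 h samples as steady-state troughs, but the documents do not say so. This objection stands, and it makes the point a mismatch between sections rather than an analysis choice. The mismatch remains, because the permitted window and the definition conflict and the SAP does not settle which governs.
- **The size is uncertain.** This also stands. The share of Day 163 visits is unknown. Patients are told that the PK procedure is mandatory on Days 21 and 161, which may keep late draws few. The half-lives are a range of mean values from a study of three doses, and the 300 mg value is not identified. SAP 3.1.1 also requires the median, minimum and maximum. A minority of low values would generally move the median less than the mean and would show in the minimum.
- **Little rests on Cmin.** No test of cycle 1 against cycle 6 is planned, and no test is specified against Phase Ib. A contrast between strata is distorted only if late draws are unevenly spread, which nothing in the documents suggests. Compliance comes from days of interruption (Protocol 12.3.3, SAP 3.12), with capsules counted at visits (Protocol 9.4.4). This stands and keeps the point minor.
- **The Study Reference Manual may deal with it.** Section 10.7 sends collection and processing details there, and it is not among the documents reviewed. It may restrict the draw, but the rule for which samples enter a summary belongs in the SAP.

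**Conclusion.** The inconsistency is real and minor. For a patient on schedule, Section 9.2.5 permits a cycle 6 draw about 48 h after the last dose, which contradicts Section 10.7 and footnote 10. No analysis rule excludes or flags it. Any such samples can bias the cycle 6 Cmin summary downward, together with the stratum summaries and the Phase Ib comparison that use it.

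Each affected sample would read about 13-37% of its 24 h trough, assuming first-order decay at the Phase Ib mean half-lives. The mean would fall by about 6-22% under the assumed 10-25% share of Day 163 draws.

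Three stronger readings are tempting but unsupported. The documents do not show that cycle 6 troughs are biased low, only that they can be. They do not make cycles 1 and 6 non-comparable in general, since Day 162 gives the same 24 h interval as Day 22. The compliance result is not at risk, because it does not use Cmin. The primary FEV₁ analysis does not use Cmin either.

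**What to change.** 1. **Protocol 9.2.5 and 10.7:** reconcile the two for the PK draw by limiting it to Days 161-162, the same one-day allowance as Day 21. Align footnote 10 with Section 10.7. The window for the other Day 161 assessments need not change.
2. **SAP 3.3 and 3.17:** state that the Cmin summary uses only samples that meet the Section 10.7 timing, about 24 h after the previous dose, with a stated tolerance (20-28 h would be one example; the documents give none). List the other samples separately with their actual time since dose.
3. **Identifying late samples:** the documents do not say that the clock time of the previous dose is recorded for each PK sample. If it is not, the last-dose date, already used for exposure (Protocol 12.3.2, SAP 3.5), set against the sampling date is enough to pick out Day 163 draws.

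The cost is a few sentences, and a few samples leave the summary. Dosing does not change.

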Question 3. Recovery after dazzling: When you transition from a semi-obscure environment to a strongly lit one, do you remain dazzled?

Questions Q1 and Q2: Y (Yes) means normal. Questions Q3: N (No) means normal.

Assessment of the extent of reported symptoms: Level 0: no abnormal answer; Level 1: one abnormal answer; Level 2: two abnormal answers; and Level 3: three abnormal answers.

NVQ administration: Screening, Day 21, Day 77, Day 161, Day 189.

Level 1 NVQ will result in the given symptom to be considered a Grade 1 AE. However, it will not trigger an escalation to Step 2. Level 2 or 3 NVQ will automatically trigger a complete ophthalmological examination (Step 2) and its AE severity graded by the ophthalmologist.

Step 2: Complete ophthalmological examination, including specific dark adaptation tests

Administration: Screening, Day 77 and Day 189, and following any Level 2-3 NVQ report.

Suggested dark adaptation test to be included: a test able to evaluate dark-adaptation changes such as cone-rod break and the final rod threshold (see note below). Severity grading using CTCAE to be performed on confirmed nyctalopia episodes. If the reported symptoms do not get confirmed by the objective measures in Step 2, the default CTCAE severity Grade 1 will be used.

Step 3: Electroretinogram (ERG)

Administration: to be performed only if clinically indicated, in particular if the ophthalmological examination results are equivocal, or the type of signs/symptoms requires it.

Ophthalmologic examinations will be performed by (or under the oversight of) a licensed ophthalmologist at screening, Day 77 and Day 189 visits. It can also be triggered on demand if a patient reports signs of ophthalmologic nature upon questioning or at the time of the scheduled ophthalmologic questions posed on several occasions, according to the Schedule of Events, page 10.

The scheduled complete ophthalmologic examination will consist of the following: Examination of visual acuity, examination for amblyopia, examination of eyelids, conjunctiva, cornea, pupillary reactions to light and accommodation, low contrast visual function (Contrast Sensitivity), specific dark adaptation testsⁱⁱⁱ, lens,

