12.5.5 Ophthalmologic Examinations and Night Vision Questionnaire

The answers to the NVQ questionnaires and the resulting Levels will be summarized by treatment group. The results (normal/abnormal, new adverse findings) of the planned post-study ophthalmologic examinations will be presented and summarized by treatment group. Ad-hoc examinations and findings will also be presented and contrasted with the baseline examination. All reported symptoms of nyctalopia and hemeralopia will be tabulated by treatment group. Reported symptoms confirmed by objective measures will be tabulated separately by treatment group. Individual data will be presented in listings.

No statistical analyses of ophthalmologic data are planned.

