3.10 Ophthalmologic Examinations and Night Vision Questionnaire

The answers to the NVQ questionnaires and the resulting levels will be summarized by treatment group. The results (normal/abnormal, new adverse findings) of the planned during- and post-study ophthalmologic examinations will be presented, alongside the baseline examination and summarized by treatment group. Ad-hoc examinations and findings will also be presented alongside the baseline examination. All reported symptoms of nyctalopia and hemeralopia will be tabulated by treatment group. Reported symptoms confirmed by objective measures will be tabulated separately by treatment group. Individual data will be presented in listings.

No statistical analyses of ophthalmologic data are planned

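### Protocol 9.2.5 item 1b triggers the eye examination on Grade 2, a scale the Night Vision Questionnaire does not produce; section 11.5 triggers it at NVQ Level 2 or 3

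*Protocol*

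**What the plan says.** Protocol 9.2.5 item 1b covers the visits on Days 21, 77 and 161. Its condition for a full ophthalmological examination is "The NVQ will be self-administered, and if Grade 2 severity criteria is met or exceeded". The same item says that on Day 77 the examination takes place whatever the questionnaire shows.

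Protocol 11.5 describes the questionnaire and the steps that follow it. There are three questions, and the result is the number of abnormal answers, Level 0 to Level 3. One abnormal answer counts as a Grade 1 adverse event and goes no further. Above that, "Level 2 or 3 NVQ will automatically trigger a complete ophthalmological examination (Step 2) and its AE severity graded by the ophthalmologist". The timing of the examination is given as "Administration: Screening, Day 77 and Day 189, and following any Level 2-3 NVQ report", and that of the questionnaire as "NVQ administration: Screening, Day 21, Day 77, Day 161, Day 189". If the examination does not confirm the symptoms, they are given Grade 1 by default. There is also an on-demand route: "It can also be triggered on demand if a patient reports signs of ophthalmologic nature upon questioning".

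The reporting sections use levels as well. Protocol 12.5.5 says "The answers to the NVQ questionnaires and the resulting Levels will be summarized by treatment group", and SAP 3.10 says the same.

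**The concern.** Grade and Level are different scales in this protocol. Grade is adverse-event severity on CTCAE. For events outside CTCAE, section 11.1.1.1 defines Grade 2 by moderate discomfort and significant interference with normal activities. Level is a count of abnormal questionnaire answers. A site that applies item 1b as written could judge two or three abnormal answers to be mild, find Grade 2 not reached, and not refer the patient, although 11.5 makes referral automatic.

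The safety stake is specific. Section 5.4.5.2 names nyctalopia as an expected effect of fenretinide, and section 7.1.2 makes safety co-primary, with particular attention to objective follow-up of reported nyctalopia. The examination is the step that confirms or refutes the symptom, and Protocol 12.5.5 reports the outcome: "Reported symptoms confirmed by objective measures will be tabulated separately by treatment group". A skipped examination leaves a reported symptom unconfirmed and can lower the count in that table.

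**Working it through.** The plan gives no figure to reproduce here. The check compares the two trigger rules and then works through the visit calendar.

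**The two rules**

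| | Protocol 9.2.5 item 1b | Protocol 11.5 |
|---|---|---|
| Scale | Grade | Level 0–3 (abnormal answers out of 3) |
| Threshold for examination | Grade 2 or above | Level 2 or 3 |
| Who assigns the grade | Not stated | Ophthalmologist, for Level 2–3 reports |
| Grade if not confirmed | Not stated | Grade 1 by default |

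Take a Level 2 or 3 result on Day 21 or Day 161. Under 11.5 the examination always follows. Under the literal text of 9.2.5 it follows only if a grade of at least 2 is already known. Section 11.5 assigns that grade at the examination, so the literal condition depends on an output of the examination it is meant to trigger. A patient not yet graded, or judged Grade 1 by the site, does not meet it. The two sections can then lead to different actions.

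**Which visits are exposed**

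- NVQ administrations (11.5): Screening, Days 21, 77, 161 and 189, so 5.
- Scheduled examinations (11.5 and the Schedule of Events): Screening, Days 77 and 189, so 3.
- NVQ administrations with no scheduled examination: 5 − 3 = 2, namely Days 21 and 161.

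**Time to the next scheduled examination if the triggered one is skipped**

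Cycles last 28 days with 21 dosing days, so dosing falls on Days 1–21, 29–49, 57–77, 85–105, 113–133 and 141–161.

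- After Day 21: 77 − 21 = 56 days. Dosing in between is Days 29–49 and 57–77, up to 21 + 21 = 42 days.
- After Day 161: 189 − 161 = 28 days, with 0 dosing days.

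The Day 161 gap matters because section 5.4.4.2 reports, from earlier long-term fenretinide trials, clear improvement in night vision after a week off drug and full resolution by one month. An abnormality present on Day 161 may no longer be confirmable on Day 189.

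**Whether other visit-level text corrects the slip**

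Item 1b has no cross-reference to 11.5. The Schedule of Events marks the examination only at the three scheduled times, and its footnote lists the components of the examination without an NVQ trigger. For Days 21 and 161, item 1b is the only trigger given in the visit procedures.

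**The case against.** The strongest reply is that this is a slip in terminology with no real conflict. Item 1b says an examination follows if a condition is met; it does not say only if. Section 11.5 independently requires the examination at Level 2 or 3, so a site following the whole protocol must perform it. The Day 77 exception in item 1b shows that the questionnaire result is the intended trigger, and that result can only be a level. The questionnaire records normal or abnormal answers and no severity, so a site would have to add a judgement of mildness that no step asks for.

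There are also backups. The on-demand route in 11.5 extends to the scheduled ophthalmologic questions, and the telephone contacts around Days 38 and 66 ask about vision. Neither 9.2.5 nor 11.5 sets a deadline for a triggered examination, so even a correctly triggered one after Day 161 could come after some recovery. Finally, the Study Reference Manual, which holds the questionnaire sheets and further detail, is not among the documents, so the wording that sites see at the point of use cannot be checked.

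Much of this stands. Grade 2 is very probably meant as Level 2, 11.5 is clear by itself, and the backups make a missed examination less likely to go unnoticed. Three things remain. The on-demand route is permissive, whereas the 11.5 trigger is automatic. The telephone contacts listed end around Day 150 and do not help after Day 161. And the visit instructions state a threshold on a scale the instrument does not have.

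**Conclusion.** The concern holds: item 1b of Protocol 9.2.5 is wrong as written, with minor impact. It uses the wrong scale for a safety trigger and is circular if taken literally. The exposure is 2 of 5 NVQ administrations. The consequence is conditional: it arises only if a site applies item 1b literally and does not apply 11.5. The gaps of 56 and 28 days count scheduled examinations only and assume that cycles run on time and that no on-demand examination takes place. The documents do not allow an estimate of how many patients would be affected. The effect is confined to ophthalmological safety monitoring and the table of confirmed symptoms; the FEV₁ analysis and the sample size are untouched.

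**What to change.** In Protocol 9.2.5 item 1b, replace the Grade 2 condition with: *NVQ Level 2 or 3 is reported (see Section 11.5)*. This changes one phrase and adds no procedure, because 11.5 already requires the examination at those levels. SAP 3.10 needs no change, since it already summarises the questionnaire by level.
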